8.2.1 Treatment modification

At the discretion of the Investigator and subject, starting with Cycle 3, Day 2, dosing may be moved to the end of the day to manage AEs (e.g. gastrointestinal).

8.2.1.1 Treatment Delay

Study drug may be taken up to 12 hours late if dosing has been delayed on a single day; otherwise that day's dose should be omitted and dosing continue on the following day. The subject should never take more than the scheduled dose on any single day.

If study drug is interrupted for more than 21 consecutive days, treatment should be permanently discontinued unless agreed in advance with Antengene.

8.2.1.2 Dose Adjustments

Dosing may be reduced or interrupted for toxicities according to [Table 4](#). Dose adjustments are to be made according to the AE showing the greatest degree of toxicity. Toxicities will be graded using the NCI CTCAE v4.03.

If considered necessary, the dose of ATG-008 should be reduced from 30 mg/d to 20 mg/day, as the first dose reduction level. If a second dose reduction is considered necessary, the ATG-008 dose should be reduced to 15 mg/day.

Continuous dose interruption of up to 2 weeks and the total discontinuation time not more than 4 weeks is allowed in this study.

Dose reduction principle for subjects who are enrolled to receive oral ATG-008 at an initial dose of 45 mg/QD or 20 mg/BID: 45 mg/QD can be reduced to 30 mg, 20 mg, 15 mg/QD; 20 mg/BID can be reduced to 15mg/BID or other doses so as to mitigate toxicity. If further dose reduction is required, it can be implemented according to the considerations of the investigator and discussion between the investigator and medical monitors of the sponsor. Dose re-escalation (higher than the initial dose is not permitted) will be allowed if the same toxicity does not recur at the reduced dose for least one cycle (4 weeks).

The dose reduction guidelines listed in [Table 4](#) below are recommended to be used for dose modifications.

Table 4: Dose Reduction Recommended Guidelines for Suspected Drug-related Toxicity

Adverse Event	Grade	Action
Thrombocytopenia	3	If bleeding present, reduce study drug one dose level.
	4	If present for more than 7 days, hold study drug until \leq grade 2. Then reduce study drug one dose level.
Neutropenia	3	If associated with fever, reduce study drug one dose level.
	4	If present for more than 7 days or associated with fever, hold study drug until \leq grade 2. Then reduce study drug one dose level.
Increased bilirubin	3	If $> 5 \times$ ULN, hold study drug until \leq grade 2. Then reduce study drug one dose level.
	4	Hold study drug until \leq grade 2. Then reduce study drug one dose level.
Transaminase increase	3	If $> 10 \times$ ULN, hold study drug until \leq grade 2. Then reduce study drug one dose level.
	4	Hold study drug until \leq grade 2. Then reduce study drug one dose level.
Stomatitis / mucositis / vomiting / diarrhea	3	If unable to control with optimal medical management within 7 days, reduce study drug one dose level.
	4	Hold study drug until \leq grade 2. Then reduce study drug one dose level.
Hyperglycemia	3 or 4	If unable to control with optimal medical management within 7 days, reduce study drug one dose level. Management guidelines provided in Appendix C (Section 19.3).

Rash	3	If fails to respond to optimal medical management within 7 days, hold study drug until \leq grade 2. Then reduce study drug one dose level.
	4	Discontinue study drug.
Pneumonitis	1	Continue study drug and monitor closely.
	2	Hold study drug until \leq grade 1. Then maintain or reduce study drug one dose level.
	3 or 4	Discontinue study drug.
Fatigue	3	If fails to respond to optimal medical management within 7 days, hold study drug until \leq grade 2. Then reduce study drug one dose level.
Other	3	Reduce study drug one dose level.
	4	Discontinue study drug.

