1.3.2.4 Preliminary Clinical Results of Study ATG-008-HCC-001

The preliminary clinical study data up to 24 May 2019 showed that a total of 33 HCC subjects were enrolled (7 subjects received oral ATG008 at the initial daily dose of 15 mg and 26 subjects received 30 mg). Subjects who were treated with ATG-008 were Asian, among which, 13 (39.4%) subjects each from China mainland and Korea, 7 (21.2%) subjects from Taiwan. Of 33 subjects, 16 (48.5%) out of them achieved SD and 13 (39.4%) achieved PD. Another 4 (12.1%) subjects still received the first cycle of treatment and no efficacy evaluation has been performed yet. DCR was 48.5% (16 subjects, 95%CI: 30.8-66.5); approximately half of the subjects (48.5%) had not reported disease progression. The median PFS was 2.0 months (95%CI: 1.9-3.8). The survivors accounted for approximately 78.8% (26/33). The median OS had not achieved (95%CI: 4.8-not achieved). The 3-month survival rate was 96% and 6-month survival rate was 58%. The diameter of the targeted lesions of tumors decreased after treatment from baseline in 42.9% (12/28 subjects) subjects. Among which, the diameter of tumors decreased >20% from baseline in 4 (14.3%) subjects.

All subjects completed the first cycle of study treatment. Subjects who received the longest treatment completed 9 cycles, with the average treatment cycles of 3.2 (± 1.6).

The most frequently reported study drug-related TEAEs were skin rash (42.4%), hyperglycemia (36.4%), decreased appetite, stomatitis and pruritus (30.3% each), diarrhea (24.2%), weight loss

(21.2%), fatigue (18.2%), platelet count decreased and white blood cell count decreased (12.1% each), and nausea, AST elevated, neutropenia, blood creatinine increased, proteinuria and hepatic dysfunction (9.1% each).

The most frequently reported Grade 3 and above study drug related TEAEs were hyperglycemia (24.2%), skin rash (18.2%), pruritus (12.1%), stomatitis (9.1%), and fatigue (6.1%).

In summary, preclinical evaluation demonstrates that overall, ATG-008 has an acceptable benefit-to-risk ratio with signals of antitumor activity observed across several tumor types, including encouraging tumor responses in sorafenib-refractory HCC. Data from the first-in-human phase 1/2 study suggest that the safety profile of ATG-008 is comparable in scope to other mTOR pathway inhibitors. Based on the aggregate safety, PK and pharmacodynamic data available, a ATG-008 dose regimen of 30 mg QD has been selected.

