12. DISCONTINUATIONS

12.1 Discontinuation from Investigational Product

The following events are considered sufficient reasons for discontinuing a subject from the study drug:

- Adverse Event(s) (that are intolerable)
- Disease progression
- Symptomatic deterioration (global deterioration of health status)
- Physician decision
- Withdrawal by subject (from treatment only)
- Death
- Lost to follow up
- Protocol violation
- Other (to be specified on CRF)

The reason for treatment discontinuation should be recorded in the CRF and in the source documents. Subjects will continue to be followed for post-treatment anticancer therapy and survival status until death.

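### Table 4 acts on bleeding at Grade 3 thrombocytopenia but not at Grade 4, so a first low-grade bleed at Grade 4 platelets has no recommended action for the first 7 days

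*Combined protocol and SAP*

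**What the plan says.** Section 8.2.1.2 sends the investigator to Table 4 for reductions and interruptions. Four cells matter here.

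- Thrombocytopenia, Grade 3: "If bleeding present, reduce study drug one dose level".
- Thrombocytopenia, Grade 4: "If present for more than 7 days, hold study drug until" Grade 2 or better, then go down one level. Bleeding is not mentioned.
- Neutropenia, Grade 4: "If present for more than 7 days or associated with fever, hold study drug until" Grade 2 or better, then go down one level. Fever is the Grade 3 neutropenia trigger, and it is repeated here.
- Other events: at Grade 3, "reduce study drug one dose level"; at Grade 4, discontinue. There is no entry for Grade 1 or 2.

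The text above the table settles which event decides: "Dose adjustments are to be made according to the AE showing the greatest degree of toxicity". The same section makes the table advisory; its guidelines "below are recommended to be used for dose modifications". Section 12.1 lists "Physician decision" among the sufficient reasons to stop study drug.

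**The concern.** Bleeding is the complication that makes a low platelet count dangerous, and it should weigh at least as heavily at Grade 4 as at Grade 3. Read as written, the table does the reverse for a time: the milder platelet grade carries an immediate recommendation and the worse grade carries none until day 8. At stake is consistent safety guidance across sites. No statistical quantity (ORR, sample size, analysis population) is affected.

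The table is likely to be used often. Section 1.4.1 reports dose reductions in 18 of 25 HCC subjects (72.0%) who started at 45 mg in the earlier trial, and the amendment brings 45 mg QD back alongside 20 mg BID. Related platelet decrease of any grade stood at 12.1% in May 2019 (Section 1.3.2.4) and 20.0% in July 2019 (Sections 1.4 and 4.2), at 15 and 30 mg. Entry is allowed with platelets down to 75 × 10⁹/L and INR up to 2.0 (Section 7.2), and stable anticoagulation is permitted (Section 9.2).

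**Working it through.** This is mainly a check of the text. The steps are to apply Table 4 to each combination of platelet grade and bleed, and then to look for another rule that fills the empty cell.

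**1. Table 4 applied case by case** (bleeds taken as suspected drug-related)

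| Situation | Recommended action |
|---|---|
| Grade 3 platelets, any bleed | Reduce one level at once |
| Grade 4 platelets, days 1–7, no bleed | None |
| Grade 4 platelets, days 1–7, first bleed of Grade 1–2 | None |
| Grade 4 platelets, Grade 3 bleed | Reduce, via the row for other events |
| Grade 4 platelets, Grade 4 bleed | Discontinue, via the row for other events |
| Grade 4 platelets, day 8 onward | Hold, then reduce |

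The third line is the gap. A duration of more than 7 days is first reached on day 8, so the window is days 1 to 7. If the word *present* in the Grade 4 cell is taken to mean the bleed rather than the thrombocytopenia, there is still no action before day 8 at the earliest.

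**2. Does another rule fill it?**

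- *Greatest-toxicity rule.* With Grade 4 platelets and a Grade 1–2 bleed, the platelet event is the more severe, so the rule leads back to the Grade 4 platelet cell.
- *Row for other events.* It starts at Grade 3.
- *Lower-grade triggers carrying upward.* The table does not say that they do, and the neutropenia rows do not rely on it, because fever is written out at both grades.
- *Section 9.2.* It gives management advice for rash, mucositis, renal insufficiency, pancreatitis and pneumonitis, but none for bleeding or low platelets.

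**3. Comparison with the other rows.** Wherever Table 4 gives actions for both Grades 3 and 4 (neutropenia, bilirubin, transaminases, the stomatitis–diarrhea group, hyperglycemia, rash, pneumonitis, other events), the Grade 4 action is at least as strong as the Grade 3 action. Thrombocytopenia is the only exception, and no reason is given.

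**4. Dose in the window.** Dose levels are from Section 8.2.1.2; the formula is doses in 7 days × mg per dose.

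- 45 mg QD: 7 × 45 = 315 mg. One level down (30 mg QD): 7 × 30 = 210 mg. Difference 105 mg; 105/315 = 33.3%.
- 20 mg BID: 14 × 20 = 280 mg. One level down, assumed to be 15 mg BID because the plan also allows other doses: 14 × 15 = 210 mg. Difference 70 mg; 70/280 = 25.0%.
- Under a hold, as in the Grade 4 neutropenia row: 0 mg while held.

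These are upper limits. They assume a bleed on day 1 and no action by the investigator all week.

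**5. Frequency.** No rate is given for Grade 4 thrombocytopenia with bleeding. In Section 1.3.2.4, "The most frequently reported Grade 3 and above study drug related TEAEs were hyperglycemia" (24.2%), skin rash (18.2%), pruritus (12.1%), stomatitis (9.1%) and fatigue (6.1%). Platelet decrease is not on that list, which points to a low frequency at 15 and 30 mg. No rate from this study is available for the two new regimens.

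**The case against.** The wording itself is not in dispute; the case against concerns its weight.

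- *Rarity.* The gap needs Grade 4 platelets, a first bleed, a bleed of only Grade 1–2, timing within 7 days, and suspected relation to the drug. A subject who already bled at Grade 3 should be one level down. Entry rules also exclude recent hemorrhagic upper GI disease. This stands, and it limits the severity.
- *Silence is not an instruction.* The Grade 4 cell neither tells the investigator to continue nor forbids a reduction. Section 8.2.1.2 allows reduction or interruption for toxicity, and Section 12.1 allows stopping. This also stands: the defect is missing guidance, not guidance to keep dosing.
- *The greatest-toxicity rule chooses between events.* It does not say that a Grade 3 trigger lapses within one event as the grade worsens, and a sensible investigator would treat the Grade 3 action as a minimum. Many would. That remains an inference each site must make for itself, and the neutropenia rows show that the table elsewhere spells the trigger out.
- *The dose figures do not measure harm.* Correct. Nothing in the documents links a 105 mg or 70 mg difference to bleeding risk; the figures only describe the exposure in question.
- *A hold goes beyond the Grade 3 action.* Also correct. Copying Grade 3 upward would mean a reduction only, and days on hold count toward the interruption limits in Section 8.2.1.2 (2 weeks continuous, 4 weeks in total). But the protocol already makes the same step from reduce to hold for febrile neutropenia at Grade 4.

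**Conclusion.** The point holds. For a first Grade 1–2 bleed in days 1 to 7 of Grade 4 thrombocytopenia, Table 4 recommends nothing, while the same bleed at Grade 3 brings a one-level reduction. From day 8 the Grade 4 action is the stronger one.

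The conclusion rests on reading each cell as complete in itself, which the neutropenia rows support, and on the bleed being too mild for the row covering other events. The clinical weight is minor to moderate: the situation should be infrequent, the table is advisory, and the investigator may act without it. Confidence in the reading of the text is high; the frequency is unknown. The cell should be corrected at the next amendment.

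**What to change.** In the Grade 4 thrombocytopenia cell, insert *or associated with bleeding* after the 7-day condition and leave the action unchanged (hold to Grade 2 or lower, then reduce one level). The cell then matches Grade 4 neutropenia. The sponsor's clinical team may prefer a stricter action.

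The cost is one line in Table 4, with no added visits, tests or subjects. The downside is possibly a few more early holds or reductions.

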8.2.2 Overdose

On a per dose basis, an overdose is defined as any amount over the protocol-specified dose of study drug assigned to a given subject, regardless of any associated adverse events or sequelae. On a frequency basis, an overdose is defined as anything more frequent than the protocol required frequency.

Complete data about drug administration, including any overdose, regardless of whether the overdose was accidental or intentional, should be reported in the case report form. See Section 11.1 for the reporting of adverse events associated with overdose.

8.3 Method of Treatment Assignment

Subjects who are in the first part of this study and are enrolled into screening period will be assigned with one available subject number. The assignment to cohort of 15mg or 30mg will be in sequence.

As for approximately 40 HCC subjects who are planned to be enrolled, subjects will be randomly assigned with one available subject number during screening period to receive oral ATG-008 at an initial dose of 45 mg/QD or 20 mg/BID.

8.4 Packaging and Labeling

ATG-008 are packaged in bottles. The study drug will be labeled per local regulations.

8.5 Investigational Product Accountability and Disposal

Antengene (or designee) will review with the Investigator and relevant site personnel the process for Investigational Product return, disposal, and/or destruction including responsibilities for the site vs. Antengene (or designee).

Investigational product containers that are returned should be retained by the site until a representative from Antengene or other Antengene-designated personnel have completed an inventory, unless otherwise agreed with Antengene. Completely used containers should be destroyed according to local guidelines, and disposition should be recorded on the Investigational Drug Accountability Record Form.

The Investigator, or a designee, shall record the dispensing of study drug to subjects in the study drug accountability record. The study drug record will be made available to Antengene, or other authorized Antengene-designated monitoring personnel for the purpose of accounting for the study drug supply. Inspections of the study drug supply for inventory purposes and assurance of proper storage will be conducted as necessary. Any significant discrepancy will be recorded and reported to Antengene or a designee and a plan for resolution will be

Investigational product will not be loaned or dispensed by the Investigator to another Investigator or site. Under certain circumstances, and with Antengene permission, cooperative groups may manage investigational product between locations within their network as clinical trial agreement and local guidelines permit.

8.6 Investigational Product Compliance

Accurate recording of all study drug administration will be made in the appropriate section of the subject's case report form (CRF) and source documents. The Investigator or designee is responsible for accounting for all study-specific study drug either administered or in their custody during the course of the study.

9. CONCOMITANT MEDICATIONS AND PROCEDURES

9.1 Recommended Concomitant Medications and Procedures

Antiviral therapy can reduce the risk of developing HCC, decrease the risk of HBV reactivation, reduce the recurrence, and improve OS and DFS of HCC patients (Ge, 2015). Therefore, antiviral therapy is required for all subjects with chronic HBV infection manifested by positive HBcAb IgM or total, positive HBsAg or HBeAg, or positive DNA-HBV viral load, or according to local practice. Standard treatment options may include entecavir, tenofovir, or telbivudine, recommended by Clinical Practice of Primary Liver Cancer 2017 (NFHPC, 2017). Lamivudine is not recommended due to higher rates of resistance in subjects with active HBV infection (HBsAg+, HBeAg+, viral load positive). Continued antiviral therapy is recommended for at least 6 months following completion of study drug treatment, or as required by local practice.

9.2 Permitted Concomitant Medications and Procedures

Over the course of this trial, additional medications may be required to manage aspects of the disease state of the subjects, including side effects from trial treatments or disease progression. In general, the use of any concomitant medication/therapies considered necessary for the care of the subject is permitted.

Prophylactic antiemetics are not required. If nausea and vomiting develop, the subject may then receive antiemetics at the discretion of the treating physician.

Stable, therapeutic doses of anticoagulants are permitted; however subjects on warfarin should have PT/INR/PTT monitored as clinically indicated.

Subjects receiving recombinant erythropoietin or darbepoetin alfa for at least 4 weeks prior to starting the study drug may continue their pretreatment doses throughout the trial.

Parenteral flu vaccination is permitted.

Anti-diabetic drugs (e.g., biguanides, insulin) are recommended to control drug-induced hyperglycemia. It is recommended that biguanides (e.g., metformin) be held 12 hours prior to and 48 hours following intravascular administration of iodinated contrast media because of their potential for acute alteration in renal function.

Treatment-related rash should be treated according to standard medical practice and Investigator judgment. Careful descriptions should be documented to help determine the nature of the rash later classification of the rash. Depending on the severity and type of rash, specific treatments may need to be administered, and study drug may need to be withheld temporarily or permanently (as described in Table 4). Treatments for rash may include non-occlusive moisturizers, topical or systemic antihistamines (e.g.,

diphenhydramine), and/or corticosteroids (with appropriate consideration to the risk of hyperglycemia). Superinfections should be cultured and appropriate topical or systemic antibiotic therapy considered.

Treatment-related mucositis and mouth ulcers should be treated as early as possible and according to standard medical practice and Investigator judgment. This may include analgesics, topical preparations (suspensions, pastes), and short courses of systemic steroids with temporary dose interruption and/or dose reduction for more severe cases. Alcohol or peroxide-containing mouthwashes should be avoided.

Acute renal insufficiency has been reported with ATG-008 and other agents in this drug class. Typically, this has been associated with drug-related gastrointestinal toxicities (anorexia, nausea, vomiting, diarrhea, mucositis) leading to dehydration and electrolyte abnormalities. Treatment with rehydration, antiemetics, and antidiarrheals is recommended, as medically indicated. Study drug dose adjustments may be used to manage these toxicities.

Drug-related pancreatitis including asymptomatic amylase and lipase elevations, as well as symptomatic pancreatitis, has been reported with ATG-008 as with other drugs in this class. Routine amylase and lipase safety lab monitoring is included in the protocol. It is recommended that subjects with symptoms of clinical pancreatitis including abdominal pain, nausea and vomiting be managed with bowel rest and pain management as medically indicated. study drug dose adjustments may be used to manage these toxicities.

Drug-related noninfectious pneumonitis, a class effect of drugs targeting the mTOR pathway, has been reported with ATG-008. The diagnosis should be considered in subjects presenting with non-specific respiratory signs and symptoms such as hypoxia, pleural effusion, cough, dyspnea, or interstitial pulmonary infiltrates, and in whom infectious, neoplastic and other causes are excluded by appropriate investigations. Those with radiological features suggestive of non-infectious pneumonitis but with minimal symptoms may continue study drug without dose alteration. Moderate symptoms may require interrupting therapy, and corticosteroids may be indicated. Once symptoms have resolved, study drug may be reintroduced at the assigned or a reduced dose level, depending on the subject's general clinical status. For severe symptoms, study drug should be discontinued and corticosteroids used until clinical symptoms have resolved.

Routine infectious disease prophylaxis (other than for HBV infection as described in Section 9.1) is not recommended. However, antibiotic, antiviral, antipneumocystis, antifungal, or other prophylaxis may be implemented during the trial at the discretion of the Investigator.

Treatment with bisphosphonates (e.g., pamidronate, zolendronate), or other agents (e.g., denosumab) to prevent or delay progression of bone metastases is permitted. Maintenance of a stable dosing regimen throughout the study is recommended.

Subjects may receive physiologic replacement doses of glucocorticoids (up to the equivalent of 10 mg daily prednisone) as maintenance therapy for adrenal insufficiency.

All concomitant treatments (treatment or prevention purpose), including blood and blood products, must be reported on the CRF.

